652 A per-protocol analysis will be performed to provide additional information regarding the
653 magnitude of the treatment effect. The per-protocol analysis will only be performed if at least
654 10% of enrolled participants would be excluded by these criteria (e.g., 5 or more participants if
655 exactly 50 are enrolled).
656 The ITT analysis is considered the primary analysis. If the results of the per-protocol and ITT
657 analyses give inconsistent results, the per-protocol analysis will be interpreted with caution. In
658 this scenario, exploratory analyses will be performed to evaluate possible factors contributing to
659 the difference.

660 **8.6 Analysis of the Primary Outcome**

661 The primary outcome of MH closure of the inner retinal layers without rescue treatment through
662 8 weeks is a binary variable that is graded by the central reading center. The proportion of eyes
663 meeting the primary outcome will be determined and the 95% Wilson (Score) confidence
664 interval will be calculated.

665 Since the chance of re-opening after closure before 8 or 24 weeks is highly unlikely, an eye with
666 MH closure of the inner retinal layers without rescue treatment at any time prior to 24 weeks will
667 be considered to have met the outcome through 24 weeks if the patient is lost to follow-up.
668 Similarly, any eye receiving rescue treatment prior to 24 weeks will be considered not to have
669 met the outcome through 24 weeks because rescue treatment has been given.

670 Multiple imputation will be used to impute missing data for eyes lost to follow-up that did not
671 have prior MH closure or rescue treatment documented. The imputation model will include
672 presence of ERM within 1 mm of the center of the macula at baseline and MH status at 1, 4, 8,
673 and 24 weeks.

674 A sensitivity analysis will be conducted using the same approach as above but without multiple
675 imputation (i.e., complete-case analysis).

676 **8.7 Analysis of the Secondary and Exploratory Outcomes**

677 The ITT analysis cohort will be used for all secondary and exploratory outcomes.

678 **8.7.1 Secondary Efficacy Outcomes**

679 Macular hole closure of the inner retinal layers without rescue treatment through 24 weeks is a
680 time-to-event outcome. A Kaplan-Meier curve will be constructed and the cumulative probability
681 with 95% confidence interval will be estimated for the final time point. Data from eyes not

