682 observed to have closure or that receive rescue treatment will be censored on the date of their
683 final visit.

684 Central VMT release without rescue treatment and central VMT release with vitreopapillary
685 traction release without rescue treatment through 24 weeks are time-to-event outcomes graded by
686 the central reading center and will be analyzed as above. The latter analysis will be adjusted for
687 vitreopapillary traction status at baseline.

688 Change in visual acuity letter score from baseline at 8 and 24 weeks is a continuous outcome.
689 The mean and 95% confidence interval will be calculated for each time point. Missing data will
690 be imputed with multiple imputation. The imputation model will include presence of ERM
691 within 1 mm of the center of the macula at baseline, baseline visual acuity, change in visual
692 acuity from baseline at 1, 4, 8 and 24 weeks, and MH status at 1, 4, 8, and 24 weeks.

693 The proportion of eyes with at least 10-letter gain (increase) or loss (decrease) in visual acuity
694 from baseline at 8 and 24 weeks are binary variables. Wilson (Score) 95% confidence intervals
695 will be calculated for each time point. The imputed data sets described above for the mean
696 change in visual acuity from baseline will be utilized.

697 The proportion of eyes receiving rescue treatment before 8 and 24 weeks is a binary variable.
698 Wilson (Score) 95% confidence intervals will be calculated for each time point. Complete-case
699 analysis (no imputation of missing data) will be used for this outcome.

700 **8.7.2 Exploratory Efficacy Outcomes**

701 The proportion of eyes with MH closure of the inner retinal layers with outer retinal lucency at 8
702 and 24 weeks is a binary variable graded by the central reading center. Wilson (Score) 95%
703 confidence intervals will be calculated for each time point. Complete-case analysis (no
704 imputation of missing data) will be used for this outcome.

705 The proportion of eyes with ellipsoid zone integrity at 8 and 24 weeks is a binary variable graded
706 by the central reading center (loss of integrity and no loss of integrity). Wilson (Score) 95%
707 confidence intervals will be calculated for each time point. Complete-case analysis (no
708 imputation of missing data) will be used for this outcome.

709 **8.8 Safety Analyses**

710 All reportable adverse events will be categorized as study eye or systemic. All events will be

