67 The ITT analysis is considered the primary analysis. If the results of the per-protocol and ITT
68 analyses give inconsistent results, then the per-protocol analysis will be interpreted with caution.
69 In this scenario, exploratory analyses will be performed to evaluate possible factors contributing
70 to the difference.

71 **1.4 Analysis of the Primary Efficacy Outcome**

72 The primary outcome of MH closure of the inner retinal layers without rescue treatment through
73 8 weeks is a binary variable that is graded by the central reading center. The proportion of eyes
74 meeting the primary outcome will be determined and the 95% Wilson (score) confidence interval
75 will be calculated.¹⁻³

76 Since the chance of re-opening after closure before 8 or 24 weeks is highly unlikely, an eye with
77 MH closure of the inner retinal layers without rescue treatment at any time prior to 24 weeks will
78 be considered to have met the outcome through 24 weeks if the participant is lost to follow-up.
79 Similarly, any eye receiving rescue treatment prior to 24 weeks will be considered not to have
80 met the outcome through 24 weeks.

81 Multiple imputation will be used to impute missing data for eyes lost to follow-up that did not
82 have prior MH closure or rescue treatment documented. The imputation model will include MH
83 status at 1, 4, 8, and 24 weeks.

84 A sensitivity analysis will be conducted using the same approach as above, but without multiple
85 imputation (i.e., complete-case analysis).

86 **1.5 Analysis of the Secondary and Exploratory Outcomes**

87 The ITT analysis cohort will be used for all secondary and exploratory outcomes.

88 **1.5.1 Secondary Efficacy Outcomes**

89 There are two time-to-event outcomes to be evaluated through 24 weeks: (1) macular hole
90 closure of the inner retinal layers without rescue treatment and (2) central VMT release without
91 rescue treatment. Each of these outcomes will be graded by the central reading center. For each
92 outcome, a Kaplan-Meier curve will be constructed and the cumulative probability of the
93 outcome with 95% confidence interval will be estimated for the final time point. Data from eyes
94 not observed to meet the outcome or that receive rescue treatment will be censored on the date of
95 their final visit (not the date of rescue treatment). The analysis of central VMT release without
96 rescue treatment will be limited to eyes with central VMT at baseline. Because the chance of re-

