97 attachment after release before 8 or 24 weeks is highly unlikely, an eye with release without
98 rescue treatment at any time prior to 24 weeks will be considered to have met the outcome
99 through 24 weeks if the participant is lost to follow-up. Similarly, any eye receiving rescue
100 treatment prior to 24 weeks will be considered not to have met the outcome through 24 weeks.

101 Change in visual acuity letter score from baseline at 8 and 24 weeks is a continuous outcome.
102 The mean and 95% confidence interval will be calculated for each time point. Missing data will
103 be imputed with multiple imputation. The imputation model will baseline visual acuity, visual
104 acuity at 1, 4, 8, and 24 weeks, and MH status at 1, 4, 8, and 24 weeks.

105 The proportions of eyes with at least 10-letter gain (increase) and least 10-letter loss (decrease)
106 in visual acuity from baseline at 8 and 24 weeks are binary variables. Wilson (score) 95%
107 confidence intervals will be calculated for each outcome at both time points. The imputed data
108 sets described above for the mean change in visual acuity from baseline will be utilized.³

109 The proportion of eyes receiving rescue treatment before 8 and 24 weeks is a binary variable.
110 Wilson (score) 95% confidence intervals will be calculated for each time point. Complete-case
111 analysis (no imputation of missing data) will be used for this outcome.

112 **1.5.2 Exploratory Efficacy Outcomes**

113 The proportion of eyes with MH closure of the inner retinal layers with outer retinal lucency at 8
114 and 24 weeks is a binary variable graded by the central reading center. Wilson (score) 95%
115 confidence intervals will be calculated for each time point. Complete-case analysis (no
116 imputation of missing data) will be used for this outcome.

117 The proportion of eyes with ellipsoid zone integrity at 8 and 24 weeks is a binary variable graded
118 by the central reading center (loss of integrity and no loss of integrity). Both ellipsoid zone
119 integrity within 1 mm of the center of the macula and in the foveal center will be analyzed.
120 Wilson (score) 95% confidence intervals will be calculated for each time point. Complete-case
121 analysis (no imputation of missing data) will be used for this outcome.

122 **1.6 Safety Analyses**

123 All reportable adverse events will be categorized as study eye or systemic. All events will be

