194 order to handle visits occurring on the border of two windows: 8 weeks, 24 weeks, 4 weeks, 1
195 week.

196 **Table 1. Analysis Windows**

Visit \pm Protocol Window	Target	Analysis Window
1 week (-4 days to +3 days)	7 days	1 day – 2 weeks (1 – 14 days)
4 (± 1) weeks	28 days	2 – 6 weeks (14 – 42 days)
8 (± 2) weeks	56 days	6 – 18 weeks (42 – 126 days)
24 (± 4) weeks	168 days	18 – 40 weeks (126 – 280 days)

197 **1.14 Missing Data**

198 The strategy for handling missing data generally is included with the description of each
199 analysis. For analyses using multiple imputation, the Markov chain Monte Carlo (MCMC)
200 method with 100 imputations will be used. Where otherwise not specified, only participants with
201 non-missing data will be included in analyses.

202 **1.15 Outliers**

203 To ensure that statistical outliers do not have an undue impact on analyses of continuous
204 outcomes, change in continuous outcomes from baseline will be truncated to ± 3 standard
205 deviations based on the overall mean and standard deviation at 8 weeks. Truncation will occur
206 after imputation, where applicable.

207 **1.16 Model Assumptions.**

208 All model assumptions will be verified. If model assumptions are seriously violated, covariates
209 may be categorized or excluded, and a non-parametric approach, robust method, or
210 transformation may be considered.

211 **1.17 Revisions**

212 Owing to lower than anticipated final sample size, the following key changes were made to the
213 analysis plan after review of study data:

214 • Presence of epiretinal membrane has been removed as a covariate from all imputation
215 and regression models.

216 • Proportion of eyes with central VMT release and vitreopapillary traction (VPT)
217 release without rescue treatment at 24 weeks has been removed from the list of
218 secondary outcomes.

219 In addition, subgroup effects will still be analyzed with logistic regression, but the subgroup
220 effect will be summarized with a risk difference instead of a relative risk.

221 References

222 1. Brown LD, Cai TT, DasGupta A. Interval estimation for a binomial proportion.
223 *Statistical Science*. 2001;16(2):101-117.

224 2. Wilson EB. Probable inference, the law of succession, and statistical inference. *Journal*
225 *of the American Statistical Association*. 1927;22(158):209-212.

226 3. Lott A, Reiter JP. Wilson Confidence Intervals for Binomial Proportions With Multiple

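### Eyes given rescue treatment are fixed as not meeting the 24-week outcome, yet the Kaplan-Meier rule lets them leave the risk set at their own last visit, which can only raise the estimate

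*SAP*

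**What the plan says.** SAP 1.5.1 introduces the outcomes with "There are two time-to-event outcomes to be evaluated through 24 weeks: (1) macular hole" closure and central VMT release, both without rescue treatment. A Kaplan-Meier curve is drawn for each, and the cumulative probability of the "outcome with 95% confidence interval will be estimated for the final time point. Data from eyes" that are "not observed to meet the outcome or that receive rescue treatment will be censored on the date of" "their final visit (not the date of rescue treatment). The analysis of central VMT release without" (the last words begin the next sentence). Protocol 8.7.1 has the same rule for eyes not "observed to have closure or that receive rescue treatment will be censored on the date of their" final visit.

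The status of a rescued eye is settled elsewhere in the plan. For VMT release, SAP 1.5.1 says that any eye receiving rescue "treatment prior to 24 weeks will be considered not to have met the outcome through 24 weeks". SAP 1.4 says the same for closure. Protocol 8.6 counts such an eye as not having "met the outcome through 24 weeks because rescue treatment has been given".

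On timing, Protocol 4.1 allows the 24-week visit at 24 ± 4 weeks (days 140 to 196). SAP 1.13, Table 1, gives a target of 168 days and an analysis window of "18 – 40 weeks (126 – 280 days" from enrollment). Neither document ties one of these days to the Kaplan-Meier estimate.

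**The concern.** Censoring tells the estimator that an eye's later status is unknown and that it would have gone on to succeed at the same rate as the eyes still under observation. For a rescued eye the plan says the opposite: its 24-week result is known, and it is a failure. If that eye drops out of the risk set before a later event, the event is divided among fewer eyes and the cumulative probability rises.

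The parenthesis about the date of rescue suggests that the authors saw this problem and meant to keep rescued eyes at risk. The rule achieves that only when a rescued eye's last visit is no earlier than the last event. An eye that has had vitrectomy and stops attending, or whose 24-week visit falls early in the window, defeats it.

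At stake are the 24-week rates for the first two secondary outcomes listed in SAP 1.2.2. The error runs in the favourable direction.

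**Working it through.** **Scale from the plan.** Protocol Table 1 gives a 95% half width of 12.3% for 50 eyes at 70% closure. The Wilson formula reproduces it: 1.96 × √(0.7 × 0.3/50 + 1.96²/(4 × 50²)) / (1 + 1.96²/50) = 0.1327/1.0768 = 12.3 points. The figures below should be read against that width.

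**Inputs.**
- From the documents: N = 50 planned (Protocol 8.3.2), 24-week visit on days 140 to 196 (Protocol 4.1), target day 168 (SAP Table 1).
- Assumed, because the documents do not give them: 40% (20 eyes) meet the outcome early; n = 30 eyes remain open; k outcomes are first seen at the 24-week visit; L rescued eyes, all among the open eyes, are last seen before that visit; no unrescued losses; visit date unrelated to outcome.

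**Direction.** Each event multiplies the event-free probability by (1 − d/r), with d events among r eyes at risk. Removing a known failure lowers r, which lowers the factor and raises the cumulative probability. With event dates fixed, the effect is never negative.

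**Rescued eyes that leave early, nominal visit times.** The curve ends at 1 − 0.6 × (1 − k/(30 − L)). With rescued eyes kept at risk it ends at 1 − 0.6 × (1 − k/30), the crude proportion.

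| k | L | Rescued eyes censored at last visit | Rescued eyes kept | Difference (points) |
|---|---|---|---|---|
| 1 | 5 | 1 − 0.6 × 24/25 = 42.4% | 42.0% | +0.4 |
| 1 | 10 | 1 − 0.6 × 19/20 = 43.0% | 42.0% | +1.0 |
| 3 | 5 | 1 − 0.6 × 22/25 = 47.2% | 46.0% | +1.2 |
| 3 | 10 | 1 − 0.6 × 17/20 = 49.0% | 46.0% | +3.0 |

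The difference simplifies to (k/N) × L/(n − L). It depends on the number of late outcomes and on the fraction of open eyes that were rescued and have gone. The early success rate enters only through n. As an example nearer to VMT release, with 41 of 50 eyes released early (n = 9), one late release and three rescued eyes gone, it is (1/50) × 3/6 = +1.0 point.

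**Rescued eyes that attend, curve read at day 168.** Actual visit dates were simulated as uniform on days 140 to 196, 20,000 trials per case. The estimate with rescued eyes censored at their visit date was compared with the estimate with them kept to day 168. The mean difference was +0.2 points (10 rescued, k = 1), +0.7 (15 rescued, k = 3) and +0.9 (20 rescued, k = 3).

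**When it vanishes.** If no outcome is first seen after a rescued eye's last visit, no factor changes and the difference is zero.

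**The case against.** The strongest reply is that the rule was deliberate and nearly works. Censoring at the final visit rather than at rescue does keep most rescued eyes at risk, and a censored eye is never counted as an event, which agrees with its being a failure. That stands as far as it goes: no rescued eye is scored as a success. It does not remove the problem, because an eye can inflate the curve simply by leaving the denominator.

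The reply can add that late outcomes are probably few. The closure series cited in Protocol 8.3.1 report results at one month or within 9 weeks, gas is expected to resolve at about 6 to 8 weeks, and vitrectomy is discretionary after 8 weeks (Protocol 4.2.1). For closure, SAP 1.2.2 also tabulates closure without rescue at 24 weeks, so a gross mismatch would be visible. Both points stand and limit the importance. The tabulation covers only closed eyes, however, so VMT release without closure has no such check.

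A reader might infer something stronger: that with no day named for the final time point, the curve could be read at its last observed date. Under the same assumptions the estimate would then exceed the crude proportion by 6.0 points on average with one late outcome and 15.1 with three, and would sometimes reach 100%. The documents do not support taking that as the plan. The outcomes are defined through 24 weeks and the 24-week target is 168 days, so day 168 is the natural reading. The unnamed day, and the choice between actual and nominal visit dates, are missing detail rather than error.

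**Conclusion.** The censoring rule conflicts with the plan's own definition of a rescued eye's result and can bias both 24-week estimates upward. The effect is small: about +0.2 to +0.9 points on average if rescued eyes attend and the curve is read at day 168, +0.4 to +3.0 points if 5 to 10 leave early with 1 to 3 late outcomes, and possibly zero. The numbers rescued, leaving early or succeeding late are all assumed. The final sample was smaller than the planned 50 (SAP version table), and for given counts of late outcomes and departures each would weigh more.

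Severity is minor. The outcomes are secondary, SAP 1.1 sets no hypotheses, and the 8-week primary outcome does not use this curve. It would be wrong to infer from this point that the reported rates are grossly inflated.

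**What to change.** In SAP 1.5.1, and in the same terms in Protocol 8.7.1, state: *An eye that receives rescue treatment before its 24-week visit, without having met the outcome before rescue, is counted as not meeting the outcome and stays in the risk set to the 24-week horizon, whatever the date of its last visit.* Timing rescue by the 24-week visit matches SAP 1.2.2.

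As a minor clarification, add: *The horizon is the 24-week visit at its nominal 168 days. Findings at that visit take the nominal time, and findings at unscheduled visits take the nominal time of the Table 1 analysis window in which they fall. Events precede censoring at ties.* With no unrescued losses, the estimate then equals the crude 24-week proportion.

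One clause needs the authors' confirmation. Read literally, the present text counts any rescued eye as not meeting the outcome, including one that met it first and was rescued later. The wording above would count that eye's earlier outcome. If the literal rule is intended, drop the clause and hold every rescued eye at risk as a non-event.

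The cost is a few sentences and minor programming, with no new data. The reported rate may fall slightly if rescued eyes left before a later outcome.

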 - 31 ▪ MH closure with central VMT release with rescue treatment
 - 32 ▪ MH closure without central VMT release with rescue treatment
- 33 • Mean change in visual acuity letter score from baseline at 8 and 24 weeks.

34 • Proportion of eyes with at least 10-letter gain (increase) in visual acuity from baseline at
35 8 and 24 weeks.

36 • Proportion of eyes with at least 10-letter loss (decrease) in visual acuity from baseline at
37 8 and 24 weeks.

38 • Proportion of eyes receiving rescue treatment before the 8-week visit.

39 • Proportion of eyes receiving rescue treatment before the 24-week visit.

40 ○ For purposes of description only, the following will be tabulated without
41 statistical comparison:

42 ■ Proportion of eyes receiving rescue treatment before the 24-week visit or
43 for which rescue treatment is planned at the 24-week visit and medical
44 records confirm rescue treatment occurred within the subsequent 12
45 weeks.

46 ■ Type of rescue treatment.

47 **1.2.3 Exploratory Outcomes:**

48 • Proportion of eyes with MH closure of the inner retinal layers with outer retinal lucency*
49 without rescue treatment at 8 and 24 weeks.

50 • Proportion of eyes with ellipsoid zone* integrity at 8 and 24 weeks.

51 ○ Both ellipsoid zone integrity within 1 mm of the center of the macula and at the
52 foveal center will be analyzed

53 *Determined by masked grader at the central reading center.

54 **1.3 Analysis Cohorts**

55 • Intention-To-Treat (ITT) Analysis Cohort: all enrolled participants irrespective of
56 treatment received.

57 • Safety Analysis Cohort: all enrolled participants irrespective of treatment received.

58 • Per-Protocol Analysis Cohort: only participants who complete the initial treatment (PVL)
59 and do not receive any non-protocol treatments during follow up. Vitrectomy performed
60 according to the criteria in section 4.2.1 of the protocol is considered per protocol and
61 eyes receiving this procedure will be included in the per-protocol cohort.

62 The primary analysis will follow the ITT principle and include all enrolled participants.

63 A per-protocol analysis will be performed to provide additional information regarding the
64 magnitude of the treatment effect. The per-protocol analysis will only be performed if at least
65 10% of enrolled participants would be excluded by these criteria (e.g., 5 or more participants if
66 exactly 50 are enrolled).

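### The rescue-treatment outcome has two unreconciled cut-offs and an undefined complete-case set; a dated event is better reported as cumulative incidence at day 56 and day 168

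*SAP*

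**What the plan says.** The outcome list in SAP 1.2.2 sets the cut-off at a visit: "Proportion of eyes receiving rescue treatment before the 8-week visit" and "Proportion of eyes receiving rescue treatment before the 24-week visit". The analysis text in SAP 1.5.1 sets it at a time: "The proportion of eyes receiving rescue treatment before 8 and 24 weeks is a binary variable". Protocol 8.4 and 8.7.1 carry the same split.

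For the interval, SAP 1.5.1 states: "Wilson (score) 95% confidence intervals will be calculated for each time point". For missing data it specifies a complete-case "analysis (no imputation of missing data) will be used for this outcome". The same section opens with: "The ITT analysis cohort will be used for all secondary and exploratory outcomes". It does not say which eyes count as complete for rescue. SAP 1.11 does spell out a complete-case set, but for the subgroup analyses of the primary outcome: eyes that attend the 8-week visit, or that closed or were rescued before 8 weeks.

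The other two 24-week event outcomes in SAP 1.5.1, hole closure and VMT release, are estimated by Kaplan-Meier. Table 1 in SAP 1.13 gives the 8-week analysis window as "6 – 18 weeks (42 – 126 days") and the 24-week window as "18 – 40 weeks (126 – 280 days"). The protocol visit window is 8 ± 2 weeks (Protocol 4.1), and a protocol visit takes priority within an analysis window.

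**The concern.** Rescue happens on a date. An eye rescued on day 50 and lost on day 60 is a known rescue. An eye lost unrescued on day 100 gives 100 days of information. A binary complete-case analysis either treats these two eyes unequally or discards information from both.

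The position of the cut-off matters because the vitrectomy rule in Protocol 4.2.1 changes at 8 weeks, so rescues may cluster where the two wordings diverge. The protocol summary names the rescue proportion as a key secondary outcome, and Protocol 1.2 says the results should help physicians and patients decide whether to try PVL before surgery. SAP 2.0 expects fewer eyes than planned, so each reclassified or dropped eye weighs more: 1/50 = 2 points at the planned size, 1/25 = 4 points at 25 eyes.

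**Working it through.** **Scale.** The only precision figures in the documents are in Protocol Table 1, for hole closure. The Wilson half-width is z√[p(1−p)/n + z²/(4n²)] / (1 + z²/n) with z = 1.96. At n = 50 it gives 9.86, 12.32 and 13.36 points for 85%, 70% and 50%, matching the stated 9.9%, 12.3% and 13.4%. No rescue rate or loss rate is stated, so all such values below are assumptions.

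**The two cut-offs.** Read 8 weeks as day 56. The protocol window is then days 42 to 70.

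| Eye | 8-week visit | Rescue | Before the visit? | Before day 56? |
|---|---|---|---|---|
| A | day 65 | day 60 | yes | no |
| B | day 50 | day 54 | no | yes |

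Both visits are in window, and the wordings disagree in both directions.

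For size, assume a constant rescue hazard from day 28 with 20% rescued by day 56, so F(d) = 1 − 0.8^((d−28)/28). This gives 10.6% at day 42, 20.0% at day 56 and 28.4% at day 70. Each figure supposes that every eye is cut off on that day, so 10.6% and 28.4% are extremes. With visits spread evenly over days 42 to 70, the average is 1 − (0.8^0.5 − 0.8^1.5)/(−ln 0.8) = 1 − 0.1789/0.2231 = 19.8%. The aggregate shift is therefore small when visits are balanced around the target. The disagreement for individual eyes remains.

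**Loss, reading (i): rescued-then-lost eyes kept, unrescued lost eyes dropped.** Assume constant hazards over 24 weeks from injection and loss independent of rescue. Let r = −ln(1−p) for rescue and c = −ln(1−loss) for loss.
- Rescued before loss: O = [r/(r+c)](1 − e^−(r+c)).
- Still followed and unrescued: S = e^−(r+c).
- Complete-case proportion: O/(O+S).

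Example with p = 30% and loss 10%: r = 0.357, c = 0.105, S = 0.70 × 0.90 = 0.630, O = 0.772 × 0.370 = 0.286. The proportion is 0.286/0.916 = 31.2%.

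| True 24-week rescue | Loss 10% | Loss 20% |
|---|---|---|
| 30% | 31.2% | 32.6% |
| 45% | 46.4% | 48.1% |
| 60% | 61.5% | 63.1% |

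The excess is 1.2 to 3.1 points. Starting the rescue hazard at day 28 instead, a true 40% at 24 weeks becomes 41.2% or 42.5%. A true 40% at 8 weeks, with 10% or 20% lost by then, becomes 40.7% or 41.5%.

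**Loss, reading (ii): completers only.** Under independent loss, the proportion is p(1−loss)/(1−loss) = p. There is no bias, but eyes rescued before being lost are thrown away.

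**Outcome-dependent loss.** Only bounds apply. With 50 eyes, 20 rescued and 5 lost unrescued, the complete-case figure under reading (i) is 20/45 = 44.4% (Wilson 30.9% to 58.8%). The bounds are 20/50 = 40% and 25/50 = 50%.

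**The case against.** The strongest reply is that this is a descriptive secondary outcome in a single-arm study without hypotheses, and that a loss effect of 1 to 3 points is well inside a Wilson half-width of about 13 points at 50 eyes. That stands as a limit on importance. It is not a reason to leave the cut-off and denominator open, since the interval does not cover a shifting definition.

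The complete-case set in SAP 1.11 applies to rescue only by analogy. It also keeps eyes that closed and were then lost. Counting those as unrescued would offset part of the upward bias, which the calculation above does not credit.

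A visit anchor has a purpose: it matches the 8-week table of closure by rescue. Under a day-56 cut-off, an eye assessed rescue-free on day 44 and rescued on day 50 counts as rescued. An eye rescued on day 60 before a day-65 assessment does not. This is right, and is why the visit-based counts should stay. It is also right that Kaplan-Meier assumes non-informative censoring and would not cure outcome-dependent loss, hence the bounds. The plan partly covers late rescue already, by tabulating rescues planned at the 24-week visit and confirmed within 12 weeks.

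A reader might infer from Table 1 in SAP 1.13 that the 8-week rescue figure can include events up to day 126. The SAP never says that the window limits set the rescue cut-off, and an in-window protocol visit falls by day 70.

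**Conclusion.** The point holds at moderate size. The plan gives two cut-offs that can classify one eye differently, and leaves the complete-case set for rescue undefined. Under one natural reading the proportion is about 1 to 3 points too high, given independent loss of 10-20% and constant hazards. Under the other, independent loss gives no bias but known information is lost. Kaplan-Meier uses partial follow-up whichever reading was meant, and the SAP already uses it for two comparable outcomes.

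Two stronger readings are not supported. The rescue figures cannot be called biased by loss as a fact, because the documents give neither the amount nor the pattern of loss. Nor do they lack a time reference: SAP 1.5.1 names 8 and 24 weeks. The defect is that this is not reconciled with the visit wording.

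**What to change.** 1. Reconcile the cut-off in SAP 1.2.2 and 1.5.1, with matching edits to Protocol 8.4 and 8.7.1.
2. Estimate the cumulative incidence of first rescue as 1 minus Kaplan-Meier from the injection date, censoring unrescued eyes at last contact. Report it with 95% confidence intervals at day 56 and day 168.
3. Keep the visit-based crude counts as description, with the denominator stated, so that they agree with the 8-week closure-by-rescue table.
4. Show bounds that count all eyes lost without rescue first as unrescued, then as rescued.

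The cost is a small extra analysis and edits in four places. Rescue dates appear to be available, since the censoring rule in SAP 1.5.1 refers to them. SAP 2.0 was itself revised after study data were reviewed, so this change should be recorded in SAP 1.17 as made after data review.
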